1.2 Study Design

This is a Phase III, randomized, multicenter, double-blind, placebo-controlled study to evaluate the efficacy and safety of durvalumab adjuvant therapy compared to placebo in patients with stage II-III non-small cell lung cancer (NSCLC) who have undergone curative intent therapy (complete resection ± neoadjuvant and/or adjuvant therapy), who have no evidence of RECIST 1.1- defined disease recurrence, and who become minimal residual disease-positive (MRD+) during a 96-week surveillance period.

Prior to CSP V2.0, the study was designed to screen approximately CCI patients and randomize approximately CCI MRD+ patients with stage II-III NSCLC whose tumors are epidermal growth factor receptor (EGFR) and anaplastic lymphoma kinase (ALK) wild type,

and who have completed curative intent therapy. Randomized patients were to include approximately **CC1** PD-L1 TC \geq 1% and **CC1** PD-L1 TC<1% patients.

Following the decision to close recruitment early, a total of 416 patients have signed informed consent for the study and approximately 30 are expected to be randomized within the study.

Eligible patients will be enrolled in a 96-week surveillance period during which they will be monitored for the emergence of MRD. During surveillance, the patient will be evaluated for MRD by plasma sampling every 6 weeks (q6w \pm 3d) and will receive computed tomography (CT) scans every 12 weeks (q12w \pm 1w) for up to 96 weeks.

Patients who become MRD+ during surveillance (including cases where analysis of the first plasma sample collected [marking the start of surveillance] returns an MRD+ status) will undergo a second screening period. Note: Patients who received prior neoadjuvant immunotherapy must be MRD- based on analysis of the first plasma sample collected (which marks the start of surveillance).

MRD+ patients will be randomized 1:1 to treatment with durvalumab monotherapy 1500 mg or placebo every 4 weeks (q4w) intravenously (IV). Randomization will be stratified by PD-L1 status (TC<1% vs TC \geq 1%), time from start of surveillance to emergence of MRD (\leq 6 months vs >6 months), and prior neoadjuvant immunotherapy (Yes vs No).

[figure not shown]
Patients will be treated for up to a total of 24 months (26 cycles), until disease recurrence, or until other specific treatment discontinuation criteria are met (whichever comes first).

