3. PRIMARY AND SECONDARY VARIABLES

3.1 Derivation of RECIST Visit Responses

For this adjuvant study, where patients with no evidence of disease at baseline (as assessed by CT/magnetic resonance imaging [MRI]) will be entered in the study, the definition of new lesions (NLs) in RECIST 1.1 is used for the assessment of disease recurrence.

For all patients, the RECIST tumour response data will be used to determine each patient's visit response according to RECIST version 1.1. It will also be used to determine if and when a patient has progressed in accordance with RECIST.

Baseline radiological tumour assessments are to be performed no more than 28 days + 7 days prior to randomization and ideally as close as possible to the date of randomization. Tumour assessments are then performed every 8 weeks \pm 1 week following randomization until week 48, and then every 12 weeks \pm 1 week until unequivocal disease recurrence or primary DFS analysis. Upon detection of disease recurrence, an additional follow-up scan should be performed 4 to 8 weeks later and evaluated using post-progression radiological criteria.

If an unscheduled assessment is performed, and the patient has not had disease recurrence, every attempt should be made to perform the subsequent assessments according to the original

imaging visit schedule (relative to the date of randomization). If a dose delay of study treatment (i.e. durvalumab/placebo) occurs, RECIST scans should continue according to the original imaging visit schedule. This schedule is to be followed in order to minimise any unintentional bias caused by some patients being assessed at a different frequency than other patients.

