3.2 Efficacy Variables

3.2.1 Disease-Free Survival (DFS)

Disease-free survival as assessed by the Investigator is the primary endpoint in this study and is defined as the time from the date of randomization until any one of the following events below, whichever occurs first, regardless of whether the patient withdraws from randomized therapy or receives another anti-cancer therapy prior to disease recurrence (i.e., date of DFS event or censoring – date of randomization + 1 day):

- Date of disease recurrence using Investigator assessments according to RECIST 1.1
 - Local, regional, or distant disease recurrence
 - Diagnosis of a second primary NSCLC
- Date of death from any cause

Disease recurrence should be based on the finding of an unequivocal NL. However, if a NL is initially equivocal (i.e. where an equivocal lesion converts to unequivocal), then the progression date should be backdated to the post-baseline follow-up scan when the NL first appeared without an intervening period of lesion absence. If equivocal lesions are present at baseline, they will not be documented on the baseline eCRF.

Patients who have not experienced disease recurrence and are alive at the time of DCO will be censored at the latest date of assessment from their last evaluable RECIST 1.1 assessment.

However, if the patient experiences disease recurrence or dies after 2 or more missed visits, the patient will be censored at the latest evaluable RECIST 1.1 assessment prior to the 2 missed visits (note: an NE visit is not considered a missed visit). Given the scheduled visit assessment scheme (i.e. every 8 weeks \pm 1 week after randomization for the first 48 weeks, then every 12 weeks \pm 1 week thereafter until appearance of disease recurrence or until

primary DFS analysis) the definition of 2 missed visits will change. The definitions are shown in [Table 3](#).

Table 3 Definition of Two Missed Visits

Previous RECIST assessment	Two missed visits (duration)	Explanation
Study day < 274 (week 39)	18 weeks	$2 \times 8 \text{ weeks} + 1 \text{ week for an early assessment} + 1 \text{ week for a late assessment} = 18 \text{ weeks.}$
Study day 274 to < 344 (>week 39 to < week 49)	22 weeks	Over this period, the scheduled frequency of RECIST assessments changes from q8w to q12w. Take the average of 8 and 12 weeks which gives 10 weeks. $2 \times 10 \text{ weeks} + 1 \text{ week for an early assessment} + 1 \text{ week for a late assessment} = 22 \text{ weeks.}$

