Study day 344 onwards (week 49)	26 weeks	$2 \times 12 \text{ weeks} + 1 \text{ week for an early assessment} + 1 \text{ week for a late assessment} = 26 \text{ weeks.}$

RECIST Response Evaluation Criteria in Solid Tumours; q8w Every 8 weeks; q12w Every 12 weeks.

If the patient has no evaluable assessments or does not have baseline data, they will be censored at day 1 unless they die within 2 visits of baseline (i.e. 17 weeks [$2 \times 8 \text{ weeks} + 1 \text{ week for a late assessment}$]), then they will be treated as an event with the date of death as the event date. Additionally, patients with unequivocal evidence of disease at baseline (as assessed by the Investigator) will be censored at randomization (day 1).

The primary endpoint analysis of DFS on the FAS analysis set will be based on Investigator assessments according to RECIST 1.1. The DFS time will always be derived based on scan/assessment dates and not visit dates.

RECIST 1.1 assessments/scans contributing toward a particular visit may be performed on different dates. The following rules will be applied:

- For Investigator assessments, the date of disease recurrence will be determined based on the earliest of the RECIST assessment/scan dates of the component that indicates disease recurrence.
- When censoring a patient for DFS, the patient will be censored at the latest of the scan dates contributing to a particular overall visit assessment.

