4.2.2 Disease-Free Survival (DFS)

4.2.2.1 Primary Analysis of DFS

Disease-free survival, using Investigator assessment according to RECIST 1.1, will be summarized, for the FAS. This will include the number (%) of patients with event or censored, along with the reason for event/censoring. Kaplan-meier curves will also be produced.

DFS data on the PD-L1 $\geq 1\%$ analysis set will be listed only.

Supportive Summaries

Additionally, a summary of time to MRD+ emergence during surveillance may be provided and this may also be included in the DFS supportive listing.

The location of the disease recurrence (local/regional, distant or second primary NSCLC) will be summarized by treatment group.

Additionally, summary statistics will be presented for the number of days from censoring to DCO for all censored patients. A summary of the duration of follow-up will be summarized using time from randomization to date of censoring (date last known to have not had disease

recurrence or died) in censored patients only (patients who have not had disease recurrence or died), presented by treatment group.

A summary table of first subsequent cancer therapies relative to recurrence by treatment group will be provided.

All the collected RECIST 1.1 data will be listed.

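### SAP Table 3 gives a Week 48 scan a 22-week limit instead of 26, so missing Week 60 alone counts as two missed visits and a Week 72 recurrence is censored at Week 48

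*SAP*

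**What the plan says.** DFS by Investigator assessment in the FAS is the primary endpoint. CSP 9.4.1.2 and SAP 3.2.1 share a censoring rule: "if the patient experiences disease recurrence or dies after 2 or more missed visits", the patient is censored at the last evaluable scan before the gap. SAP 3.2.1 adds that a visit assessed as not evaluable is not a missed visit.

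Scans are every 8 weeks "following randomization until week 48, and then every 12 weeks", each with a one-week margin either side (SAP 3.1; CSP 8.1.1 agrees). After Week 48 the scheduled scans are therefore Weeks 60, 72, 84 and so on.

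SAP Table 3 turns two missed visits into a duration that depends on the last scan:

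- "Study day < 274 (week 39": 18 weeks, from 2 × 8 + 1 + 1.
- "Study day 274 to < 344 (>week 39 to < week 49": 22 weeks. The stated reasoning is "Take the average of 8 and 12 weeks which gives 10 weeks", then 2 × 10 + 1 + 1.
- "Study day 344 onwards (week 49": 26 weeks, from 2 × 12 + 1 + 1.

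SAP 4.2.2.1 reports DFS as the "number (%) of patients with event or censored, along with the reason for event/censoring", with Kaplan-Meier curves.

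**The concern.** The averaging behind the 22-week row assumes that one 8-week and one 12-week interval lie ahead. That is true after Week 40. After Week 48 no 8-week interval remains, yet nearly the whole Week 48 window falls in the 22-week row.

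The two boundaries also follow different conventions. Day 274 (Week 39) is the early edge of the Week 40 window, whereas day 344 (Week 49) is the late edge of the Week 48 window. The matching early edge would be day 330 (Week 47).

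The consequence is a censoring after one missed visit where the rule asks for two. A recurrence at Week 72 becomes a censoring about 24 weeks earlier, reported with a reason that is untrue. The error can only remove events, so from Week 72 onward the Kaplan-Meier curve of the arm concerned is the same or higher than it should be.

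**Working it through.** **Inputs.** Scan schedule from SAP 3.1 and 3.2.1; limits and day boundaries from SAP Table 3. Randomization is day 1, so the study day of Week *w* is 7*w* + 1, and each scan window is that day ± 7. A gap counts as two missed visits when it exceeds the limit.

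**Reproducing the table.** 2 × 8 + 2 = 18, 2 × 10 + 2 = 22 and 2 × 12 + 2 = 26 weeks, that is 126, 154 and 182 days. Day 274 = 7 × 39 + 1 and day 344 = 7 × 49 + 1. The table's arithmetic is correct.

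**Limit needed at each visit** = weeks to the second next visit + 2. For each last scan, all 15 × 15 = 225 in-window day pairs were checked for a patient who misses one visit and has the event at the next.

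| Last scan | Next two intervals | Limit needed | Table 3 limit | Pairs censored after one missed visit |
|---|---|---|---|---|
| Weeks 8-32 | 8 + 8 | 18 | 18 | 0 of 225 |
| Week 40 | 8 + 12 | 22 | 22 | 0 of 225 |
| Week 48 | 12 + 12 | 26 | 22 (days 330-343); 26 (day 344 only) | 210 of 225 |
| Weeks 60-120 | 12 + 12 | 26 | 26 | 0 of 225 |

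**Week 48 in detail.** With scans exactly on schedule, Week 48 to Week 72 is 505 − 337 = 168 days, or 24 weeks: over 22, under 26. The Week 72 window is days 498-512. For Week 48 scans on days 330-343 the gap runs from 498 − 343 = 155 to 512 − 330 = 182 days. All 14 × 15 = 210 pairs exceed 154 and none exceeds 182.

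**Deaths and unscheduled scans.** A death is wrongly censored only if it comes more than 22 weeks after the Week 48 scan and before the Week 72 window closes: for a scan on day 337, from 337 + 154 + 1 = day 492 to day 512. A recurrence found on an unscheduled scan within 22 weeks is kept.

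**With the boundary at day 330.** One missed visit is censored in 0 of 225 pairs at every visit. Two missed visits are still caught in 225 of 225 pairs, including Weeks 60 and 72 missed with an event at Week 84.

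**Expected number of patients.** The documents give no accrual dates by patient, no site dates for CSP v2.0 and no missed-scan rate, so these are assumptions: 15 patients per arm, even accrual to 25 May 2022, exponential DFS with the planned FAS median of 4 months on placebo and 4/0.63 = 6.35 months on durvalumab (CSP 9.2), and 5-10% missing Week 60.

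- Week 48 is 11.04 months and Week 72 is 16.56 months.
- S(48) − S(72) is 0.148 − 0.057 = 0.091 on placebo and 0.300 − 0.164 = 0.136 on durvalumab.
- With full follow-up, 15 × (0.091 + 0.136) = 3.4 events fall between Weeks 48 and 72.
- That is multiplied by the share of patients randomized early enough to reach Week 71 (497 days), the opening of the Week 72 window, and by 5-10%.

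| First patient randomized | Scans run to | Share reaching Week 71 | Patients affected |
|---|---|---|---|
| 1 Jan 2021 | 23 Mar 2023 (SAP approval) | 0.617 | 0.11-0.21 |
| 1 Jan 2021 | 21 Nov 2022 (IDMC#1) | 0.377 | 0.06-0.13 |
| 1 Jan 2021 | 2 Aug 2022 (CSP v2.0 date) | 0.159 | 0.03-0.05 |
| 21 Nov 2021 | 23 Mar 2023 | 0 | 0 |

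The last row takes first dosing as 12 months before IDMC#1, in line with the review trigger in SAP 5.2; Week 71 then falls on 2 April 2023.

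**The case against.** The case against concerns importance, not arithmetic.

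- **Nothing turns on it.** Under CSP v2.0 every analysis is descriptive, and "approximately 30 are expected to be randomized within the study". There is no test or hazard ratio for DFS. This stands and limits the point to a small correction.
- **The upper estimate is generous.** It needs a first randomization in January 2021, which rests on a planning date, and protocol scans up to SAP approval, whereas CSP 10.1 stops study assessments when CSP v2.0 is implemented at a site. The timing of IDMC#1 suggests a later start, which gives zero or nearly zero. This also stands.
- **210 of 225 is not a risk.** It describes only patients who had a Week 48 scan, missed Week 60 and recurred at Week 72. Agreed: it shows that the misclassification is systematic in that situation, not that the situation is common.
- **An affected patient would be visible**, since censoring reasons are summarized and all RECIST data are listed. True, but someone would have to look, and the summary count and curve would still be wrong.
- **The CSP sets no duration, and Table 3 is the SAP's chosen approximation.** The CSP does leave the duration open. But its rule is stated in visits, and a duration that triggers after one missed visit does not implement it. The averaging argument applies only to Week 40.
- **The bias is not uniform.** Early censoring also shrinks the risk set, so between Weeks 48 and 72 the curve is equal or lower if others have events. Correct; it is equal or higher only from Week 72.

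**Conclusion.** Wrong as written, with a practical effect that is probably nil. Table 3 matches the scan schedule at every visit checked except Week 48, where it treats one missed visit as two for a scan on any day of the window but the last. The conclusion rests only on the schedule and the table's own formula. It assumes that the randomization-based schedule (8-weekly to Week 48, then 12-weekly) applies to all randomized patients; the 12-weekly wording for early discontinuers in CSP 7.1.1 is read as an editorial inconsistency.

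The size, 0 to about 0.2 patients, rests on the assumptions listed with the calculation, and the lower end fits the IDMC timing better. If a case did occur it would show: under the planned medians and with no earlier censoring, about 15 × 0.148 = 2 placebo and 15 × 0.300 = 4-5 durvalumab patients are still event-free at Week 48, so each late event is a large step in the curve.

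**What to change.** In SAP Table 3, move the last boundary from day 344 (Week 49) to day 330 (Week 47):

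- study day < 274: 18 weeks
- study day 274 to < 330: 22 weeks
- study day 330 onwards: 26 weeks

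Make the same change in the DFS derivation program before the analysis. If the analysis has already been run, rerun it and report any patient whose event or censoring status changes. No other rule needs to change.

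The cost is one day limit in the table and in the program, with no new data and no site contact. The trade-off is slight: after a Week 48 scan on days 331-343, an event up to 13 days after the Week 72 window closes (343 + 182 = day 525 against day 512) would be kept, for example a recurrence on an unscheduled scan. The table already allows that tolerance at the other visits.

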#### **8.1.1.2 Dating of recurrence**

Dating of recurrence should always be based on the first onset of a sign but never on the onset of a symptom. The date of first detection of a palpable lesion is acceptable only when the diagnosis of tumor involvement is subsequently established. The diagnosis of recurrent disease by radiographs or scans should be dated from the date of the first positive record, even if this is determined in retrospect, or tissue confirmation occurs subsequent to the initial appearance of a suspicious area/lesion on a scan.

If there is equivocal progression and the site staff is unsure whether to consider this a DFS event, the medical monitor/study physician should be contacted.

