#### **9.4.1.2 Primary endpoint: disease-free survival**

DFS is defined as the time from the date of randomization until the date of disease recurrence (local, regional, or distant disease recurrence or second primary NSCLC) using Investigator assessments according to RECIST 1.1, or date of death due to any cause, whichever occurs first.

Patients who are disease-free, ie, have not experienced disease recurrence, and alive at the time of analysis will be censored at the latest date of assessment from their last evaluable RECIST 1.1 assessment. However, if the patient experiences disease recurrence or dies after 2 or more missed visits, the patient will be censored at the latest evaluable RECIST 1.1 assessment prior to the 2 missed visits. If the patient has no evaluable assessments or does not have baseline data, they will be censored at Day 1 unless they die within 2 visits of baseline, then they will be treated as an event with the date of death as the event date. The primary endpoint analysis of DFS will be based on Investigator RECIST 1.1 assessments.

The DFS time will always be based on scan/assessment dates and not visit dates.

DFS rate at 6 and 12 months is defined as the proportion of patients alive and disease-free at 6 and 12 months respectively, estimated from Kaplan-Meier plots of the primary endpoint of DFS.

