2.1.1 Full Analysis Set

The FAS will include all randomized patients. The FAS will be used for all efficacy analyses including patient-reported outcomes (PROs). Treatment groups will be compared on the basis of randomized study treatment, regardless of the treatment actually received. Patients who were randomized but did not subsequently receive study treatment are included in the analysis in the treatment group to which they were randomized.

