2.2 Protocol Deviations

The following general categories will be considered important protocol deviations (IPDs) and will be listed and discussed in the CSR as appropriate:

- Inclusion criteria deviations: Patients who deviate from inclusion criteria 2, 6, 11 and/or 13 per Section 5.1 of the CSP.
- Exclusion criteria deviations: Patients who deviate from exclusion criteria 4 and/or 13 per Section 5.2 of the CSP.
- Discontinuation criteria for study product met but patient not withdrawn from study treatment.
- Investigational product (IP) deviation:
 - (a) Patient received incorrect IP to that to which they were randomized.
 - (b) Patients who were randomized but did not receive IP.
- Excluded medications taken: Received prohibited concomitant systemic anti-cancer therapy.
- Deviations related to study procedure: Baseline RECIST scan > 49 days before randomization.

Patients who receive the wrong treatment at any time will be included in the safety analysis set as described in Section 2.1. During the study, decisions on how to handle errors in treatment dispensing (with regard to continuation/discontinuation of study treatment or, if applicable, analytically) will be made on an individual basis with written instruction from the study team leader and/or statistician.

The IPDs will be listed and summarized by randomized treatment group. IP deviation of patients who were randomized but did not receive IP will lead to exclusion from the safety analysis set. None of the other deviations will lead to patients being excluded from the analysis sets described in Section 2.1. A per-protocol analysis excluding patients with specific IPDs is not planned.

The programmatic determination of the IPDs above will be a separate process outlined in the study Protocol Deviations Plan, which will also include full details regarding IPDs as well as the activities and responsibilities related to the IPD process.

In addition, other study deviations captured from the eCRF module for inclusion/exclusion criteria will be tabulated and listed. Any other deviations from monitoring notes or reports may be reported in an appendix to the CSR.

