6. CHANGES OF ANALYSIS FROM PROTOCOL

The following are changes from the planned analyses described in version 2 of the CSP.

Overall visit response table updated to more accurately reflect RECIST 1.1 evaluations and responses applicable to this study.

Except that change, this SAP has been produced in line with section 10.4 of CSP V2.0, which states:

“Under CSP v2.0, as a result of the decision by AstraZeneca to close enrollment to the study and end study assessments early, all analyses of the objectives and endpoints listed in Section 3 will be descriptive only and considered exploratory. Further details will be included in the SAP.”

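### Patients randomized with disease at baseline are censored at Day 1 for primary DFS even when they are known to have died, and the SAP does not declare this rule as a change from the protocol

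*SAP*

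**What the plan says.** SAP 3.2.1 has two Day-1 censoring rules for DFS, one after the other.

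- The first covers patients with no evaluable assessment or no baseline data: "they will be censored at day 1 unless they die within 2 visits of baseline". The SAP spells the window out as 17 weeks, and such a death is an event on its own date.
- The second covers patients who had disease at entry: "Additionally, patients with unequivocal evidence of disease at baseline (as assessed by the Investigator) will be censored at randomization (day 1". It carries no clause about death.

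The same section defines the DFS event as recurrence or death, whatever the cause of death. SAP 1.1.1 sets the primary objective as DFS in everyone randomized, and SAP 2.1.1 says "The FAS will include all randomized patients".

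Unequivocal recurrence on baseline imaging breaches exclusion criterion 4 (protocol 5.2). SAP 2.2 makes that breach an important protocol deviation. Apart from never-dosed patients, who leave the safety set, it adds: "None of the other deviations will lead to patients being excluded from the analysis sets described in Section 2.1".

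Protocol 9.4.1.2 uses Day-1 censoring only when a patient has no evaluable assessment or "does not have baseline data, they will be censored at Day 1 unless they die within 2 visits of baseline". It says nothing about disease found at baseline.

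SAP Section 1 promises that changes to protocol specifications will be described in Section 6. Section 6 names one: "Overall visit response table updated to more accurately reflect RECIST 1.1 evaluations and responses applicable to this study".

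**The concern.** A patient who is in the FAS but has no follow-up is counted in the denominator of the event table and has no influence on the curve. For this group the SAP discards outcomes it may know. A death needs no disease-free baseline to be interpreted, and it is half of the DFS definition. As written, a patient with a baseline scan and a recorded early death is treated less completely than a patient with no baseline scan at all.

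Patients with visible disease at entry are plausibly among the first to fail. Setting their time to one day is therefore likely to lift the curve of whichever arm they are in, and the result would still be labelled DFS in all randomized patients. A reader who compares the protocol with SAP Section 6 would not learn that the rule had been added.

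**Working it through.** **1. The Day-1 rules side by side**

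| Situation | Protocol 9.4.1.2 | SAP 3.2.1 | Early death counted? |
|---|---|---|---|
| No evaluable assessment, or no baseline data | Day 1 | Day 1 | Yes: within 2 visits, 2 × 8 + 1 = 17 weeks in the SAP |
| Unequivocal disease at baseline | No rule | Day 1 | No |

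The second row is new in the SAP and is missing from its Section 6.

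**2. What Day-1 censoring does to the curve**

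Take 15 patients in an arm. Two are censored at Day 1 and 13 have events at days 60, 90, 120 and so on.

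- At day 60 there are 13 at risk, so S = 12/13 = 0.9231.
- At day 90, S = 11/13 = 0.8462. At day 120, S = 10/13 = 0.7692.
- Deleting the two patients and recomputing gives the same numbers at risk and the same S at each of these times.

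For the Kaplan-Meier estimate, then, Day-1 censoring is deletion.

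**3. Planning inputs**

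The only effect-size figures in the documents come from the superseded design (protocol 9.2): placebo median 4 months, exponential DFS, HR 0.63 in the FAS.

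- Median gain: 4/0.63 − 4 = 2.3 months, as stated.
- Events for 90% power at two-sided 5%: 4 × (1.960 + 1.282)² / (ln 0.63)² = 197, as stated.

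The planning values are therefore read correctly. They serve below only as an illustration.

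**4. Possible size**

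SAP 1.2 expects about 30 randomized, 1:1. I take 15 per arm, so each patient is 1/30 = 3.3% of the FAS. The documents do not give the number k with baseline disease in an arm, so I assume a range of 0 to 3 and assume that each such patient fails before 6 months.

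- Placebo, violators censored: S(6) = 0.5^(6/4) = 0.354.
- Placebo, violators counted: S(6) = (15 − k)/15 × 0.354.
- Durvalumab, violators censored: S(6) = 0.5^(0.63 × 6/4) = 0.519, with the same multiplier when they are counted.

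| k in the arm | Placebo, 6-month DFS | Durvalumab, 6-month DFS |
|---|---|---|
| 0, or all censored at Day 1 | 35.4% | 51.9% |
| 1 counted | 33.0% | 48.5% |
| 2 counted | 30.6% | 45.0% |
| 3 counted | 28.3% | 41.6% |

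In the placebo arm one patient moves the estimate by about 2 points and two move it by about 5.

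**The case against.** **The endpoint is hard to define for these patients.** SAP 3.1 uses the new-lesion definition because patients are meant to enter without disease, and SAP Table 2 has only rows with target and non-target lesions marked not applicable. If the sentence were simply deleted, a patient whose baseline tumour grew without new lesions would never have a recurrence and would stay on the curve as disease-free. This stands: simple deletion is not a sound remedy. It does not explain why deaths are dropped.

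**Little is lost overall.** Event and censoring counts are given with reasons and all RECIST data are listed (SAP 4.2.2.1). OS is listed (4.2.3), all deaths in the FAS are tabulated (4.2.9.1), and exclusion 4 deviations are listed and summarized by arm (2.2). This also stands. A reader might infer that the patients leave the FAS or that their outcomes vanish from the report, and the documents do not support that. The loss is confined to the DFS time variable and its curve.

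**The weight is small.** Imaging is required before randomization and waivers are barred, so there may be no such patient. No test or hazard ratio is planned, and a 6-month rate is not a named output. With 13 patients the standard error of a 35.4% estimate is about √(0.354 × 0.646/13) = 13 points, larger than any shift in the placebo column. All true. It limits the importance of the point, not its correctness.

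**The protocol leaves detail to the SAP** (9.5 and 10.4). It does, but SAP Section 1 undertakes to record changes to protocol specifications in Section 6, and a new censoring rule for the primary endpoint is one.

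**A stronger reading that fails.** Protocol 8.1.1.2 says recurrence seen on scans "should be dated from the date of the first positive record, even if this is determined in retrospect". A reader might infer that a Week-8 recurrence traced back to the baseline scan would turn from an event into a Day-1 censoring, so that a post-randomization finding drives the rule. SAP 3.1.1 and 3.2.1 limit backdating to post-baseline scans, and 3.2.1 adds that equivocal baseline lesions are not documented on the baseline form. The trigger is unequivocal disease at baseline as the Investigator judged it. Nothing in the documents shows that the rule favours one arm.

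**Conclusion.** The point holds in a limited form. SAP 3.2.1 removes randomized patients with unequivocal, Investigator-assessed baseline disease from the primary DFS curve and ignores even their known deaths. That is at odds with the SAP's own DFS definition and with the rule next to it. It has no counterpart in protocol 9.4.1.2 and is not declared in SAP Section 6.

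If such a patient exists, the curve in that arm is likely to be too favourable. The illustrated size is 35.4% against 33.0% (one patient) or 30.6% (two) for 6-month DFS on placebo. This rests on 15 per arm, a 4-month exponential median and failure of each such patient before 6 months. The number affected is not in the documents and may be zero. Equivocal baseline lesions are outside the rule. Because the analysis is descriptive, the consequence is a possibly flattering curve and an undeclared rule, not a wrong test result.

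**What to change.** 1. In SAP 3.2.1, give these patients at least the death exception of the neighbouring rule: censor at Day 1 unless the patient dies within 2 visits of baseline (17 weeks), in which case the death is a DFS event on its date.
2. Add one supportive Kaplan-Meier display for the FAS in which they stay at risk from randomization. The event is the first post-randomization Investigator-assessed progression (including growth of the baseline lesion), new lesion or death. State how progression is scored, since SAP Table 2 does not cover patients with baseline lesions; protocol Appendix G has target and non-target criteria that could be cited. Report the number affected per arm beside both curves.
3. Declare the baseline-disease rule in SAP Section 6 as a change from protocol 9.4.1.2.

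The cost is a few lines of SAP text and one more programmed display. If such patients exist, the DFS curve may look less favourable. If there are none, the display can be replaced by a statement that the count is zero in each arm.
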